5.6. Retest management during screening period

A patient who has a laboratory result that does not satisfy the entrance criteria may have the test repeated providing that the investigator judges it relevant according to the patient previous result or medical history and if s/he considers laboratory abnormalities are likely to be transient. Results of the test(s) repeated should be obtained within the allowed screening period. In this case the patient will not be required to sign another informed consent and the original patient identification number assigned by the investigator will be used.

In any case, the last result available for each parameter must be considered for the patient inclusion.

5.7. Additional information recorded at the inclusion visit

Not applicable

5.8. Patient withdrawal

5.8.1. Withdrawal criteria

Information to be collected during the last visit of these patients is given in [section 5.8.2](#). These follow-up modalities are used to ensure the efficacy and safety evaluation of all patients who received the IMPs.

The reasons for premature discontinuation of IMPs are:

- **Adverse events** incompatible with continuation of one of the IMPs according to the judgment of the investigator, including no recovery in safety parameters. Criteria for treatment discontinuation are implemented during the LID period in order to avoid treating a patient in medical condition that could jeopardize his/her safety or interfere with the conduct of the study. If the patient cannot receive the LID2 or the first S64315 C1D2 dose due to an AE, the S64315 infusion (either LID2 or C1D2) may be postponed by 1 to 5 days. If the LID2 is postponed for more than 2 days (5 days maximum), the C1D2 dose may not be postponed for more than 2 days. If S64315 C1D2 is postponed, azacitidine C1D1 dose should be postponed as well, whenever possible. If the AE has not recovered within this time period, the patient must be withdrawn from the study.
- **Pregnancy** (for reporting, see [section 8.9.2.3](#))
- **Protocol deviation** if it interferes with the study evaluations and/or if it jeopardises patient's safety, e.g. any medical event requiring administration of an unauthorised concomitant treatment (see [section 6.3](#))
- **Disease progression** at the discretion of the investigator
- **Treatment failure**, defined as failure to achieve CR, CRi, MLFS or PR after at least 6 cycles of study treatment
- **Non-medical reason** (to be thoroughly described) e.g. consent withdrawal, patient's removal
- **Other, physician decision** (for reasons that cannot be included in any of the criteria listed above, for example: availability of a better therapeutic alternative for the patient)

If the patient becomes eligible for transplant, patient treatment discontinuation should be left to the investigator's decision.

If the patient is benefiting from the study treatment according to the investigator's judgement and if it is in the patient's best interest to continue the combination of S64315 with azacitidine, the patient may remain on study treatment. A patient must discontinue the combination if the toxicity recurs with the same or worse severity after resumption of dosing, unless the investigator decides it is in the patient's best interest to continue the combination of IMPs and upon documented agreement with the Sponsor.

If one IMP is permanently discontinued, both drugs should be permanently discontinued. A patient must be withdrawn from the study if one the IMPs is interrupted for more than 28 consecutive days from C1D2, for any reason. However, for patients with LVEF decline, IMP interruptions of up to 35 consecutive days are permitted.

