Table (4.1.3.5) 2 - Non evaluability criteria

Permanently discontinued treatment before C1D28 for reasons other than DLT
Did not undergo a DLT assessment at the end of Cycle 1
Did not receive the minimum exposure criteria i.e. minimum number of doses according to the dose administration schedule of both IMPs prescribed from study entry to DLTs assessment visit (end of Cycle 1 D28), unless treatment was stopped for a DLT - see Table (4.1.3.5) 3
If a patient received more than the assigned IMP doses from study entry to DLT occurrence during the DLT assessment period, non-evaluability criteria will be reassessed by Sponsor and investigator - see Table (4.1.3.5) 3

Table (4.1.3.5) 3 - Minimum number of S64315 and azacitidine doses to meet minimum exposure until the end of cycle 1

Schedule description	Minimum number of doses
S64315 during the 2-week LID period (LID1 on D-13 and LID2 on D-6)	2 out of 2
S64315 (D2, D9, D16 and D23 in 28-day cycle)	3 out of 4
Azacitidine (D1 to D7 in 28-day cycle)	5 out of 7

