4.4. Discontinuation of the study

4.4.1. Premature discontinuation of the study or temporary halt

This study may be temporarily halted or prematurely discontinued at any time for any sufficient reasonable cause. Stopping rules during the study are described in [section 8.12](#) for any patient throughout the study, in [section 10.2.7](#) for the dose escalation phase I part, in [section 10.3](#) for the expansion phase II part and in [section 4.4.2](#). Moreover, the DSMB could also give recommendations, based on the review of the safety data, to suspend or to prematurely terminate the study/treatment arms in case of serious concerns about patient safety.

After having informed the coordinator, the sponsor or the Institutional Review Board (IRB)/Independent Ethics Committee (IEC) or the Competent Authorities may terminate the study before its scheduled term. Two copies of the written confirmation will be dated and signed by the coordinator. The IRB/IECs and Competent Authorities will be informed according to local regulations.

If the study is prematurely discontinued, the ongoing patients should be seen as soon as possible, and the same assessments as described in [section 5.8](#) should be performed.

Under some circumstances, the investigator may be informed of additional procedures to be followed, in order to ensure that adequate consideration is given to the protection of the patient's interests.

In case of study suspension (temporary halt), the study may resume once concerns about safety, protocol compliance and data quality are addressed and satisfy the Sponsor, the Institutional Review Board (IRB)/Independent Ethics Committee (IEC) and Competent Authorities.

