8.12. Management of treatment dose adaptations due to toxicities

For patients who do not tolerate the protocol-specified dosing schedule, dose interruptions and/or reductions are either recommended or mandated in order to allow patients to continue the study treatments.

Dose modifications recommendations for S64315 are summarised in [Table \(8.12\) 1](#).

A patient must discontinue treatment with S64315 if, after treatment is resumed at a lower dose, the toxicity recurs with the same or worse severity, unless in the opinion of the investigator it is in the patient's best interest to continue S64315, and upon documented agreement with the Sponsor.

For each patient, once a dose reduction has occurred, the dose may not be re-escalated during the subsequent cycles unless in the opinion of the investigator it is in the patient's best interest to continue S64315, and upon documented agreement with the Sponsor.

When a patient meets the criteria for S64315 discontinuation described in the table, he/she must discontinue both IMPs.

Dose modifications for azacitidine must be done according to azacitidine E.U. SmPC (see [Table \(8.12\) 2](#)).

These dose changes must be recorded in the eCRF.

Table (8.12) 1 - Criteria for interruption and re-initiation of S64315

Recommended dose modifications for S64315	
Worst toxicity CTCAE Grade^a (unless otherwise specified)	During a cycle of therapy
Investigations (Renal)	
Serum creatinine	
Grade 2 (> 1.5 – 3 x ULN or > 1.5 – 3 x baseline)	Omit dose until resolved to Grade ≤ 1 or baseline, then: - If resolved in ≤ 14 days, then maintain dose level - If resolved in > 14 days, then ↓ 1 dose level
Grade 3 (> 3 – 6 x ULN or > 3 x baseline)	Omit dose until resolved to Grade ≤ 1 or baseline, then ↓ 1 dose level
Grade 4 (> 6 x ULN)	Discontinue patient from test drug treatment
Note: If intercurrent illness, e.g. dehydration due to diarrhoea or febrile infections, leads to prerenal insufficiency, this should not be considered drug related and the criterion for dose modification not fulfilled	
Investigations (Hepatic)	
Isolated Total Bilirubin elevation^b	
Grade 2 (> 1.5 - 3.0 x ULN if baseline was normal, >1.5 - 3.0 x baseline if baseline was abnormal)*	Omit dose until resolved to Grade ≤ 1, then: - If resolved in ≤ 14 days, maintain dose - If resolved in > 14 days, ↓ 1 dose level

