Grade 3 (> 3.0 - 10.0 x ULN)	Omit dose until resolved to Grade ≤ 1, then: - If resolved in ≤ 14 days, ↓ 1 dose level - If resolved in > 14 days, discontinue patient from test drug treatment The patient should be weekly monitored (including Liver Function Tests (LFT) ^f), or more frequently if clinically indicated, until total bilirubin has resolved to baseline or stabilised over 4 weeks
Grade 4 (> 10.0 x ULN)	Discontinue patient from test drug treatment The patient should be weekly monitored (including LFT), or more frequently if clinically indicated, until total bilirubin has resolved to baseline or stabilised over 4 weeks
Isolated AST or ALT elevation	
AST or ALT > 3.0 – 5 x ULN	Omit dose S64315 until resolved to ≤ 3 x ULN, then maintain dose
Grade 3 (> 5.0 - 20.0 x ULN if baseline was normal; >5.0 - 20.0 x baseline if baseline was abnormal)	Omit dose until resolved to ≤ 3 x ULN, then: - If resolved in ≤ 14 days, maintain dose - If resolved in > 14 days, ↓ 1 dose level.
Grade 4 (> 20.0 x ULN if baseline was normal; >20.0 x baseline if baseline was abnormal)	Discontinue patient from test drug treatment

Combined^c elevations of AST or ALT and total bilirubin^e

AST or ALT > 3.0 x ULN combined with total bilirubin > 2.0 x ULN and confirmed Hy's law cases according to FDA guidance

- For patients with normal baseline ALT or AST or total bilirubin value
 - If AST or ALT > 3.0 x ULN combined with total bilirubin > 2.0 x ULN without evidence of cholestasis^d:
 - Permanently discontinue patient from test drug treatment For patients with elevated baseline AST or ALT or total bilirubin value
 - If [AST or ALT > 2.0 x baseline AND > 3.0 x ULN] OR [AST or ALT > 8.0 x ULN], whichever is lower, combined with [total bilirubin > 2.0 x baseline AND > 2.0 x ULN]:
 - Permanently discontinue patient from test drug treatment.
- Repeat LFT^f as soon as possible, perform liver imaging to assess biliary tract or liver disease (if possible), preferably within 48h from awareness of the abnormal results, then with weekly monitoring of LFT^f, or more frequently if clinically indicated, until AST, ALT or bilirubin has resolved to baseline or stabilised over 4 weeks

Investigation (Pancreatic)**Amylase and/or lipase elevation**

Grade 1 (> ULN - 1.5 x ULN)	May maintain dose level
> 1.5 - 2.0 x ULN	May maintain dose level

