> 2.0 - 5.0 x ULN and asymptomatic	Omit dose until resolved to Grade ≤ 1 or baseline then: 
 - If resolved in ≤ 14 days, maintain dose level - If resolved in > 14 days, ↓ 1 dose level
Grade 3 (> 2.0 - 5.0 x ULN with signs or symptoms or >5.0 x ULN and asymptomatic)	Discontinue patient from test drug treatment
Grade 4 (> 5.0 x ULN and with signs or symptoms)	Discontinue patient from test drug treatment

Note: A CT scan to assess the pancreas, liver, and gallbladder must be performed within 1 week of the first occurrence of any Grade ≥ 3 amylase and/or lipase, or as clinically indicated

Investigation (Metabolic)**Creatine (phospho)kinase elevation**

Grade 3	Omit dose until resolved to Grade ≤ 2, then: 
 - If resolved in ≤ 14 days, maintain dose level - If resolved in > 14 days, ↓ 1 dose level
Grade 4	Omit dose until resolved to Grade ≤ 2, then: 
 - If resolved in ≤ 14 days, then ↓ 1 dose level - If resolved in > 14 days, then discontinue patient from test drug treatment

Gastro intestinal	
Pancreatitis	
Grade \geq 3	Discontinue patient from test drug treatment
Diarrhoea	
Grade 1 and 2 ^g	Maintain dose level, treat the patient per institutional diarrhoea management protocol
Grade 3	Omit dose until resolved to Grade \leq 1, treat the patient per institutional diarrhoea management protocol, then: 
 - If resolved in \leq 5 days, maintain dose level - If resolved in $>$ 5 days despite the use of optimal anti-diarrhoea therapy, \downarrow 1 dose level
Grade 4	Discontinue patient from test drug treatment.
Grade \geq 3 Vomiting	Maintain dose level, if not resolved to Grade \leq 2 within 48h after start of optimal anti-emetic therapy, then omit dose until resolved to Grade \leq 2, and then \downarrow 1 dose level
Metabolism and nutrition disorders	
Electrolyte abnormalities (if clinically significant)	
Grade 3	Omit dose until resolved to Grade \leq 1, then: 
 - If resolved in \leq 7 days, maintain dose level - If resolved in $>$ 7 days, \downarrow 1 dose level
Grade 4	Discontinue patient from test drug treatment
Skin and subcutaneous tissue disorders	
Rash /photosensitivity	
Grade 1	Maintain dose level Consider initiating appropriate skin toxicity therapy (e.g. antihistamines and topical corticosteroids) as per local institutional guidelines Consider skin biopsy for evaluation

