Grade 3	Omit dose until resolved to Grade ≤ 1, and increase ophthalmic monitoring frequency to at least once a week, and refer the patient to an ophthalmologist within one week for further evaluation, then: 
 - If resolved in ≤ 14 days, ↓ 1 dose level - If resolved in > 14 days, discontinue patient from test drug treatment
Grade 4	Discontinue test drug treatment and refer the patient to an ophthalmologist for monitoring
Haematological abnormalities (myelosuppression)	
Neutropenia and thrombocytopenia Grade 4	If bone marrow clearance, omit dose and/or interrupt azacitidine until count recovery: 
 - If resolved in < 28 days, then maintain the dose level - If resolved in > 28 days, then consider discontinuing patients from study unless the patient has evidence of clinical benefit and in discussion with the Sponsor a decision is made to continue therapy at a lower dose
Other AEs	
Grade 3	If Grade 3 (except those correctable within 7 days and deemed by the investigator to be not clinically important), hold treatment until resolved to Grade ≤ 1 or baseline, then: 
 - If resolved in ≤ 14 days, ↓ 1 dose level - If resolved in > 14 days, discontinue patient from test drug treatment
Grade 4	Discontinue test drug treatment
NOTE In some particular cases, a patient with a Grade 3 or Grade 4 AE may resume treatment at the lower dose level if in the opinion of the Investigator and after discussion with the Sponsor, the event is not life-threatening, and the patient can be managed and monitored for recurrence of the AE. In case of TLS Grade 3 or 4, the dose adaptation of the study drugs will be discussed between the sponsor and the investigator according to the patient's benefit/risk assessment.	

All dose modifications should be based on the worst preceding toxicity.

Patients may receive supportive care (e.g. packed red blood cells) as per local institutional guidelines.

^a Common Toxicity Criteria for Adverse Events (CTCAE v5.0)

^b If Grade 3 or 4 hyper-bilirubinaemia is due to the indirect (non-conjugated) component only, and haemolysis as the aetiology has been ruled out as per institutional guidelines (e.g. review of peripheral blood smear and haptoglobin determination), then ↓ 1 dose level and continue treatment at the discretion of the investigator

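### Section 8.12 limits the stop on recurrent toxicity to lower-dose resumption, while section 5.8.1 and the synopsis apply it after any resumption; ten same-dose table rows fall in the gap

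*Protocol*

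**What the plan says.** Three places in the protocol state what follows when a toxicity comes back.

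- **Synopsis (Duration of treatment) and section 5.8.1:** "A patient must discontinue the combination if the toxicity recurs with the same or worse severity after resumption of dosing". The dose at which treatment was resumed is not specified. The exception is an investigator decision in the patient's interest, with documented sponsor agreement.
- **Section 8.12:** S64315 must be stopped if "after treatment is resumed at a lower dose, the toxicity recurs with the same or worse severity". The exception is the same.

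Table (8.12) 1 then gives an action for each toxicity. Ten rows hold S64315 and allow it to restart at an unchanged dose. For Grade 2 creatinine the row reads "If resolved in ≤ 14 days, then maintain dose level". For AST or ALT between 3 and 5 times ULN it reads "Omit dose S64315 until resolved to ≤ 3 x ULN, then maintain dose". A general note under the table adds: "All dose modifications should be based on the worst preceding toxicity".

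SAP section 4.2.1.2 lists six deviation categories. One covers patients who met a withdrawal criterion and were not withdrawn.

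**The concern.** The recurrence sentence in 8.12 does not cover recurrence after same-dose resumption, and same-dose resumption is what ten rows of its own table allow. Sites are directed to 8.12: section 4.1.3.6 for the conditions for resuming after a DLT, section 6.1.1 for dose adaptation, and section 4.4.1 for stopping rules applying to individual patients. A site that follows those pointers and meets a repeat event finds the same row and the same instruction. Under 5.8.1 that patient should stop, or continue only once sponsor agreement is documented.

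Two things are at stake. One is the sponsor's check before a patient is re-exposed to a dose that has already produced the toxicity twice. The other is deviation reporting: an undocumented continuation looks compliant under 8.12 read alone but is a missed withdrawal criterion under 5.8.1.

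The toxicities are expected ones. Section 2.2.2 names diarrhoea and rises in troponin I, ALT and AST among the most frequent adverse events, and neutropenia among the most frequent severe ones. These correspond to five of the ten rows, although that section does not give the grades the rows use.

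**Working it through.** The plan gives no figure to reproduce. The check is a comparison of texts and a count of rows.

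**Step 1: scope of the rule.**

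| Place | Trigger | Dose at resumption | Override |
|---|---|---|---|
| Synopsis, 5.8.1 | recurrence, same or worse severity | not limited | investigator plus documented sponsor agreement |
| 8.12 | recurrence, same or worse severity | lower dose only | the same |

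The only difference is recurrence after same-dose resumption. Section 5.8.1 speaks of the combination and 8.12 of S64315, but both sections tie discontinuation of one drug to the other, so that is not a second gap.

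**Step 2: rows of Table (8.12) 1 that omit the dose and then allow the same dose.**

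| Row | Resolution time for same dose | Further condition | First or repeat event distinguished |
|---|---|---|---|
| Creatinine, Grade 2 | 14 days or less | none | no |
| Total bilirubin, Grade 2 | 14 days or less | none | no |
| AST/ALT >3–5 x ULN | no limit | none | no |
| AST/ALT, Grade 3 | 14 days or less | none | no |
| Amylase/lipase >2–5 x ULN, asymptomatic | 14 days or less | none | no |
| CK/CPK, Grade 3 | 14 days or less | none | no |
| Diarrhoea, Grade 3 | 5 days or less | none | no |
| Electrolytes, Grade 3 | 7 days or less | none | no |
| Troponin, Grade 1 | 7 days or less | no LVEF fall of 10% or more | no |
| Neutropenia/thrombocytopenia, Grade 4 | under 28 days | bone marrow clearance | no |

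By time limit: 1 (none) + 1 (5 days) + 2 (7 days) + 5 (14 days) + 1 (28 days) = 10. Rows that treat a repeat differently: 0 of 10. Rows that maintain the dose without omitting it, such as Grade 1–2 diarrhoea, involve no resumption and are not counted.

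**Step 3: does other wording in 8.12 close the gap?**

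- The worst-preceding-toxicity note does not. A repeat at the same grade returns to the same row. A worse repeat can also lead back to the same dose: AST/ALT of 3–5 x ULN that recurs as Grade 3 may still resume unchanged if it resolves within 14 days.
- The table's first-occurrence wording concerns a pancreatic scan, which "must be performed within 1 week of the first occurrence of any Grade" 3 or higher amylase or lipase. Its recurrence wording concerns LVEF monitoring after a dose reduction, and resumption at the lower dose after some Grade 3 or 4 events. None of it governs the ten rows.

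**Step 4: worked case.** Grade 3 diarrhoea resolves within 5 days, S64315 restarts at the same dose, and Grade 3 diarrhoea returns. Under 5.8.1 and the synopsis, the combination stops unless continuation is agreed and documented. Under 8.12 the recurrence sentence is not triggered, and the row allows the same dose again if the episode resolves within 5 days. Neither section cites the other on this point.

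**The case against.** The strongest reply is that nothing conflicts. Section 8.12 is silent on same-dose recurrence, and silence is not permission. Section 5.8.1 is the section on withdrawal criteria, the synopsis repeats its rule, and the table describes its contents as recommended modifications. Read together, the broader rule binds. This stands: a reader might infer that 8.12 authorises continuation, and it does not. What remains is that a site can follow the section it was sent to and still miss a duty stated elsewhere.

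A reader might also take section 4.4.1 as making 8.12 the sole source of patient-level stopping rules. It does not say so. The synopsis field that lists 8.12 among the stopping rules itself contains the broader recurrence rule.

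A third inference would be that cycle 1 DLT results change. A patient is non-evaluable if he or she "Permanently discontinued treatment before C1D28 for reasons other than DLT", so a stop under 5.8.1 might remove someone whom 8.12 would keep. The documents do not establish this. The DLT criteria also include failure to restart the test drug at the same dose because of drug-related toxicity. A stop might therefore itself count as a DLT and leave the patient evaluable; how that criterion applies to a recurrence is arguable. SAP section 4.2.3.1 takes DLTs as the investigator reported them.

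Finally, the deviation category can be applied as it stands, since it follows the 5.8.1 criteria. That is correct. The difficulty is that a site relying on 8.12 would not know it had created the deviation.

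**Conclusion.** The mismatch is real and minor. One event, a same-or-worse recurrence after same-dose resumption, is covered by the stopping duty in two places and left out of it in the third, where ten rows lead back to the same dose. For a patient who continues, the practical difference is whether sponsor agreement must be documented.

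No dose decision depends on it: SAP section 1.3.1 states that escalation was stopped and that neither intra-patient escalation nor an expansion part will be conducted. The documents give no frequency of same-dose recurrence, and none can be derived. They also do not say whether any patient is still on treatment.

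The conclusion assumes that the unqualified wording in 5.8.1 means what it says and covers resumption at any dose. If the sponsor intended the narrower rule, 5.8.1 and the synopsis are too broad and are the texts to change. Either way one of them needs correcting.

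**What to change.** In section 8.12, change *resumed at a lower dose* to *resumed at the same or a lower dose*, and keep the override. Cross-refer section 5.8.1, the synopsis and section 8.12 to one another.

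Do not add a table note restricting the same-dose option to a first occurrence. That would drop both the override and the same-or-worse-severity trigger, and so create a new dosing rule. For example, it could deny same-dose retreatment to a patient with a second Grade 4 cytopenia after marrow clearance even where the sponsor agrees. If a note is wanted, it should say only that the same-dose rows are subject to the recurrence rule and its override.

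If the protocol will not be amended again, list in the study report each same-or-worse recurrence after same-dose resumption and whether sponsor agreement was documented. The SAP text describes no such listing. Under SAP section 4.2.1.5 a restart at the same dose is not counted as a dose modification.

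The cost is one phrase and the cross-references, with no added procedures or patients. The downside is that some continuations after same-dose recurrence will need documented sponsor agreement, which 5.8.1 and the synopsis already require.

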
If one drug is permanently discontinued, both drugs should be discontinued. A patient should be withdrawn from the study if one of the IMPs is interrupted for more than 28 consecutive days for any reason. However, for patients with LVEF decline, IMP interruptions of up to 35 consecutive days are permitted.
 
If the patient is benefiting from the study treatment according to the investigator's judgement and if it is in the patient's best interest to continue the combination of S64315 with azacitidine, the patient may remain on study treatment.
 
A patient must discontinue the combination if the toxicity recurs with the same or worse severity after resumption of dosing, unless the investigator decides it is in the patient's best interest to continue the combination of IMPs and upon documented agreement with the Sponsor.
 
For each patient, once a dose reduction has occurred, the dose may not be re-escalated during the subsequent cycles unless in the opinion of the investigator it is in the patient's best interest to continue S64315, and upon documented agreement with the Sponsor.
 
Criteria for treatment discontinuation during the LID period:
 
 - If the patient cannot receive the LID2 or the first S64315 C1D2 dose due to an AE, the S64315 infusion (either LID2 or C1D2) may be postponed by 1 to 5 days. If the LID2 is postponed for more than 2 days (5 days maximum), the C1D2 dose may not be postponed for more than 2 days. If S64315 C1D2 is postponed, azacitidine C1D1 dose should be postponed as well, whenever possible. - If the AE is not recovered within this time period, the patient must be withdrawn from the study. 
This study may be temporarily halted or prematurely discontinued at any time for any sufficiently reasonable cause. Stopping rules are described in corresponding sections 4.4.1, 4.4.2, 8.12, 10.2.8 and 10.3.
 
The end of trial is defined as the date of the last follow-up visit of the last patient, including a phone contact, or the date of the last contact attempt if the last patient is declared lost to follow-up.
		

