6.1.2. Administration/re-administration criteria

- Criteria to fulfil before each S64315 infusion
 - Before each S64315 infusion, biological parameters should be checked in order to detect any toxicity (see [Table \(8.12\) 1](#))
 - Patients with Grade ≥ 2 hypo/hypercalcemia and/or hypo/hypermagnesia and/or hypo/hyperkalaemia despite attempts at medical correction should not be treated with S64315
 - Patients with WBC ≥ 10 G/L despite attempts at medical correction should not be treated with S64315. Hydroxycarbamide can be used to reduce the circulating blast count before and throughout the treatment period
 - AST and ALT ≤ 3 x ULN (except for LID1: AST and ALT ≤ 1.5 x ULN)
 - Total bilirubin level ≤ 1.5 x ULN, except for patients with known Gilbert's syndrome, who are excluded if total bilirubin > 3.0 x ULN or direct bilirubin > 1.5 x ULN
 - In the case of an S64315 interruption ≥ 28 days, its readministration must be preceded by a lead-in dose period (except for patients in CR/CRi) which is called additional Lead-In dose period. See [Table \(4.1.2\) 1](#) for more details on safety assessments required.
- Criteria to fulfil before each first azacitidine administration (i.e. CxD1)

Patients should be monitored for haematological toxicity and renal toxicities. A delay in starting the next cycle or a dose adjustment due to haematological toxicity and/or renal toxicity may be necessary according to E.U. SmPC (see [Table \(8.12\) 2](#)). WBC, absolute neutrophil count (ANC), platelets, serum creatinine, BUN and serum bicarbonate will be assessed before starting the next treatment cycle.

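### Withdrawal is mandatory after more than 28 days of interruption (section 5.8.1), but the Grade 4 cytopenia row of Table (8.12) 1 lets treatment continue

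*Protocol*

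**What the plan says.** **The withdrawal rule.** Protocol section 5.8.1 says that a patient *must* be withdrawn when either study drug is "interrupted for more than 28 consecutive days from C1D2, for any reason". The next sentence gives the one listed exception: "for patients with LVEF decline, IMP interruptions of up to 35 consecutive days are permitted". The synopsis (Duration of treatment) sets the same limit and the same LVEF exception in weaker words and without a starting point for the count: "A patient should be withdrawn from the study if one of the IMPs is interrupted for more than 28 consecutive days for any reason".

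**The cytopenia row.** For Grade 4 neutropenia and thrombocytopenia, Table (8.12) 1 begins: "If bone marrow clearance, omit dose and/or interrupt azacitidine until count recovery". Recovery in under 28 days leads to resumption at the same dose level. For recovery in more than 28 days, discontinuation is to be *considered*, "unless the patient has evidence of clinical benefit and in discussion with the Sponsor a decision is made to continue therapy" at a lower dose.

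**Related text.**
- Section 5.8.1 and the synopsis also say that a patient who is benefiting may stay on treatment if the investigator judges this to be in the patient's best interest. Neither says whether this overrides the 28-day rule.
- Section 4.1.1 and the synopsis allow a 4-week interruption for marrow recovery when the AML is not active, with Sponsor approval.
- Section 6.1.2 and the synopsis say that after an S64315 interruption of 28 days or more, "its readministration must be preceded by a lead-in dose period (except for patients in CR/CRi"). Section 8.2.9 requires tumour lysis prophylaxis on re-administration after an interruption of that length.

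**The concern.** A rule that is mandatory and applies whatever the reason leaves no room for an unlisted exception. A separate table then supplies one for a foreseeable toxicity. Section 2.3.4 anticipates overlapping myelosuppression, and the DLT criteria in section 4.1.3.5 include Grade 4 cytopenia persisting for 28 days. An investigator could withdraw such a patient or re-treat at a lower dose, and could cite the protocol for either.

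What is at stake is whether a patient is re-exposed after long marrow suppression, and how that patient is then reported. SAP section 4.2.1.2 has a deviation category for patients who met a withdrawal criterion and were not withdrawn. A patient continued under the table belongs in that category if section 5.8.1 governs, and does not if the table governs. The disposition summaries in SAP section 3.2.1, which give withdrawals with their reasons, depend on the same choice.

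**Working it through.** The plan gives no figure to reproduce, so the check is a comparison of day ranges.

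**1. Withdrawal rule against the cytopenia row.** Suppose first that dosing stops when the cytopenia starts and resumes at recovery, so that recovery time equals interruption time.

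| Interruption | Section 5.8.1 (no LVEF decline) | Cytopenia row | Compatible? |
|---|---|---|---|
| Under 28 days | Withdrawal not required | Resume, same dose level | Yes |
| Exactly 28 days | Withdrawal not required | No branch: the limits are < 28 and > 28 | Row is silent |
| 29 days or more | Withdrawal mandatory | Consider discontinuing; continuation at a lower dose possible | No |

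The conflict covers every duration from day 29 onward. Even without clinical benefit the row asks only for consideration, where section 5.8.1 requires withdrawal.

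**2. The two clocks.** The row counts days to resolution of the cytopenia (R). Section 5.8.1 counts days of interruption. If dosing stops k days after the cytopenia begins and resumes at recovery, the interruption lasts R − k days, and the passages conflict when R − k > 28.
- With k = 0, they conflict from R = 29.
- With k = 7 (an assumption: one weekly S64315 interval), they conflict from R = 36, since 36 − 7 = 29.

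The different clocks delay the conflict by k days and do not remove it.

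**3. How interruption days are counted.** This is not defined. Azacitidine has a planned 21-day rest in each cycle. Counted from the last dose, an 8-day cycle delay already gives 21 + 8 = 29 dose-free days. Counted from the missed Day 1, the delay itself must exceed 28 days. Both counts are assumptions, and which one is meant changes who meets the criterion.

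**4. The 4-week allowance.** 4 × 7 = 28 days, which does not exceed 28. It is compatible with section 5.8.1.

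**5. Restart conditions in sections 6.1.2 and 8.2.9 and the synopsis (28 days or more).** These can be obeyed together with section 5.8.1 at exactly 28 days, and from 28 to 35 days for LVEF decline. Beyond that (from day 29 without LVEF decline, from day 36 with it) the withdrawal rule leaves no restart for them to govern. Their text has no upper limit and does not say this.

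**The case against.** **Sponsor discussion is a central check.** Continuation under the row needs discussion with the Sponsor, so sites would not act wholly alone. That makes divergent handling less likely, but it does not settle which text governs. Section 14.2 tells investigators not to ask the sponsor to approve a deviation. If section 5.8.1 governs, the discussion in the row comes close to such a request.

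**The benefit sentence may already be a general exception.** It resembles the row's test of clinical benefit. But it stands beside a mandatory rule that admits no reason as an excuse, and its precedence is not stated.

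**The clocks differ.** This is correct, and it narrows the conflict to cases where the interruption itself exceeds 28 days.

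**Little of the trial remains.** The SAP (sections 1.3 and 1.3.1) says that escalation was stopped and expansion will not be conducted. An amendment therefore matters only for patients still on treatment. Deviation classification still needs one reading.

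**Stronger readings that a reader might infer, which the documents do not support:**
- *That sections 6.1.2 and 8.2.9 also contradict the withdrawal rule.* They set conditions for a restart and do not authorise one that section 5.8.1 forbids. They have real scope, and the 4-week allowance makes exactly 28 days a planned case.
- *That every interruption over 28 days other than for LVEF decline is affected.* The cytopenia row is the one row that addresses recovery beyond 28 days and leaves continuation open. Several others, such as Grade 3 bilirubin and QTcF prolongation, already require discontinuation if the event has not resolved within 14 days.
- *That prolonged myelosuppression is the main expected overlapping toxicity.* Section 2.3.4 says only that overlapping myelosuppression may be observed, and it also names tumour lysis syndrome and gastrointestinal disorders.
- *That the rule distorts dose intensity by itself.* SAP section 4.2.1.5 computes exposure from actual dates and doses. The rule reaches those results only through how the patient is managed.

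**Conclusion.** The protocol is wrong as written on one point. For Grade 4 neutropenia or thrombocytopenia with marrow clearance, where the resulting interruption exceeds 28 days, section 5.8.1 mandates withdrawal and Table (8.12) 1 permits continuation. In addition, exactly 28 days is unassigned in the row, the standing of the benefit sentence is unstated, and the synopsis differs from section 5.8.1 in force (*should* against *must*) and in omitting C1D2 as the start of the count.

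The documents do not give the number of patients affected. The effect is on management of those patients, disposition and one descriptive deviation category. No sample size, decision boundary or error rate changes. The conclusion assumes that the interruption itself, and not only the cytopenia, passes 28 days. It takes no position on which clinical rule is right.

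**What to change.** Reconcile section 5.8.1, the synopsis text on duration of treatment and the haematological row of Table (8.12) 1, so that one rule governs interruptions over 28 days. List its exceptions in one place and state:
- whether the benefit sentence is among them;
- what applies at exactly 28 days;
- from which day an interruption is counted, for each drug.

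Align the restart conditions in section 6.1.2, section 8.2.9 and the synopsis by stating the range of interruptions to which they apply. The sponsor must decide which rule applies; this review proposes none.

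Document the same reading for the SAP deviation category before database lock, so that patients with the same course are classified alike. The cost is wording in an amendment and a short note in the deviation specifications; no analysis has to be redesigned.
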